5.2 Inclusion/Exclusion Criteria

Prior to being enrolled, participants will fill out a screening questionnaire. The screening questionnaire will automatically qualify or disqualify them for study participation. The full screening questionnaire can be found in the Appendix. (Appendix C)

Inclusion Criteria:

Adult candidates who are in overall good health and who suffer from mild to moderate tension headaches.

Participants will be deemed to be in good health if they do not report any of the existing medical conditions asked about in the screening questionnaire.

Exclusion Criteria:

- Those who have been diagnosed with migraine headaches.
- Those who score between 36-40 or 66-78 on screening questionnaire.
- Is < 18 years of age
- Women that are pregnant or breastfeeding.
- Alcohol consumption more than 10 drinks per week.
- Chronic renal disease
- Chronic liver disease
- Allergy to any of the following: Aspirin or any other product including Salicylates, Boswellia, Feverfew, Skullcap, White Willow Bark, Rice Hull, or Vegetable Cellulose.
- Unable to swallow pills.
- Unwilling to try test product for relief of pain and tension headache symptoms.
- Participants who are currently taking any anticoagulation medications daily. (Aspirin, Warfarin, Heparin etc.)

6 Study Evaluation

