2.2.1 Potential Risk

Minimal risk is foreseen for participants through their participation in the study. All the ingredients composing the test product are Generally Recognized as Safe (GRAS) by the FDA for daily consumption at their present concentrations.

The ingredients in the test product have shown to have some theoretical drug interactions which have been listed in the appendix. (*Appendix A*)

Potential side-effects have been observed in high doses which are significantly greater than the dose of the capsule as recommended in the instruction for use:

- Diarrhea
- Nausea
- Stomach Cramps
- Acid Reflux
- Skin Rashes
- GI Bleeding
- Headaches
- Liver Damage

This study is determined by Sponsor and Principal Investigator to be a Minimal Risk Study.

Minimal risk is defined by 45 U.S. Code of Federal Regulations (CFR) 46.102 (i) as follows:

"Minimal risk means that the probability and magnitude of harm or discomfort anticipated in the research are not greater in and of themselves than those ordinarily encountered in daily life or during the performance of routine physical or psychological examinations or tests."

Refer to: http://www.hhs.gov/ohrp/humansubjects/quidance/45cfr46.htm#46.102

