13.1.1.3 ANTICOAGULANT/ANTIPLATELET DRUGS

Interaction Rating = **Minor** Be watchful with this combination.

Severity = Moderate • Occurrence = Unlikely • Level of Evidence = **B**

In vitro evidence suggests that magnesium sulfate inhibits platelet aggregation at concentrations as low as 0.5-1.0 mM (20304,20305). Some preliminary clinical evidence suggests that infusion of magnesium sulfate increases bleeding time by 48% and reduces platelet activity (20306). However, other clinical research seems to show that magnesium does not affect platelet aggregation, although inhibition of platelet-dependent thrombosis (PDT) can occur (60759). Theoretically, concomitant use of magnesium with anticoagulants or antiplatelets could increase the risk of bleeding.

Some of these drugs include aspirin, clopidogrel (Plavix), dalteparin (Fragmin), enoxaparin (Lovenox), heparin, indomethacin (Indocin), ticlopidine (Ticlid), warfarin (Coumadin), and others.

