VITAMIN D: One intestinal route of magnesium absorption is thought to be vitamin D dependent (9634). Various forms of vitamin D, including ergocalciferol, 25-hydroxycholecalciferol (calcifediol), and 1,25-dihydroxycholecalciferol (calcitriol) increase magnesium absorption; especially when taken in high doses (9634,9635,9636,9637). This effect has been used to treat hypomagnesemia in people with malabsorption syndromes (9516,9635,9636).

ZINC: Supplementation with high doses of zinc, 142 mg daily, appears to decrease magnesium absorption and magnesium balance in healthy adult males (9624). Also, moderately high dietary zinc intake, 53 mg daily, seems to increase magnesium excretion without affecting copper metabolism in postmenopausal women. This might adversely affect bone health. Zinc may compete with magnesium for ion exchange transport in the intestine (12424). More research on the clinical importance of these observations is needed.

WHITE WILLOW BARK

There is one Serious Drug Interactions known for White Willow Bark, of which it is anecdotal. Just like aspirin, White Willow Bark might increase the risk of bleeding, and so the concomitant use of anticoagulants and antiplatelet drugs should be avoided.

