13.1.1.15 ANTICOAGULANT/ANTIPLATELET DRUGS

Interaction Rating = Major Do not take this combination.

Severity = High • Occurrence = Probable • Level of Evidence = **D**

Concomitant use theoretically might increase the risk of bleeding due to decreased platelet aggregation. Willow bark has antiplatelet effects, but less so than aspirin (12810). Avoid concomitant use with other anticoagulant and antiplatelet drugs. Some of these drugs include aspirin, clopidogrel (Plavix), dalteparin (Fragmin), enoxaparin (Lovenox), heparin, ticlopidine (Ticlid), warfarin (Coumadin), and others.

```

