13.1.1.16 ASPIRIN
```

Interaction Rating = **Moderate** Be cautious with this combination.

Severity = Moderate • Occurrence = Probable • Level of Evidence = **D**

Willow bark contains salicin, a plant salicylate. Theoretically, willow bark might have an additive effect with other salicylate-containing drugs such as aspirin (12808).

```

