13.1.1.19 ANTICOAGULANT/ANTIPLATELET DRUGS
```

Interaction Rating = Moderate Be cautious with this combination.

Severity = High • Occurrence = Possible • Level of Evidence = **D**

Some evidence suggests that feverfew may inhibit platelet aggregation. However, this has not been demonstrated in humans (6935,6936,6942,6943,6944,6945,6951). Theoretically, feverfew might have additive effects and increase the risk of bleeding when used with these drugs.

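### Appendix A gives two instructions for willow bark with aspirin, and beyond the daily-use exclusion and the one-hour rule the visible text passes on neither

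*Combined protocol and SAP*

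**What the plan says.** **Appendix A.** The introduction to White Willow Bark says that "the concomitant use of anticoagulants and antiplatelet drugs should be avoided". The class entry for anticoagulant and antiplatelet drugs (13.1.1.15) is rated "Major Do not take this combination" and continues: "Avoid concomitant use with other anticoagulant and antiplatelet drugs. Some of these drugs include aspirin". The next entry, for aspirin alone (13.1.1.16), is rated Moderate, asks for caution, and gives this reason: "Theoretically, willow bark might have an additive effect with other salicylate-containing drugs such as aspirin (12808". Section 2.2.1 refers to the appendix in one sentence: "The ingredients in the test product have shown to have some theoretical drug interactions which have been listed in the appendix".

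**Screening.** Section 5.2 excludes "Participants who are currently taking any anticoagulation medications daily. (Aspirin, Warfarin, Heparin etc". Question 11 of the screening form (Appendix C) asks about the same daily use, adds the idea of blood thinning, and names aspirin.

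**Rescue and dosing.** Section 4.2, the diary reminder (Appendix E) and the visible part of the product insert (Appendix H) bar all other medication in the hour after a dose. After that hour, sections 4 and 4.2 permit other medication and except no drug. The instructions for use (Appendix B) allow two capsules up to three times a day and mention no other medicine.

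**The concern.** Participants have headaches and choose their own rescue, so aspirin is a foreseeable choice. The diary's pain scale names it beside ibuprofen as a mild painkiller at level 3; that is scale wording, not advice. The sponsor took the interaction seriously enough to exclude daily users. A person who takes aspirin only as needed passes screening, and then meets a rescue rule that conflicts with the stricter of the two Appendix A entries.

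What is at stake is a possible bleeding risk to participants. The main result is not at stake, because rescue is allowed only after the one-hour rating, the last of the primary endpoint.

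**Working it through.** No figure in the plan depends on this point. The check is a comparison of texts, followed by a count of exposure.

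**1. Appendix A against itself (willow bark).**

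| Entry | Covers aspirin? | Rating | Mechanism | Evidence level |
|---|---|---|---|---|
| 13.1.1.15, class entry | Yes, first drug named | Major: not to be combined | Reduced platelet aggregation, bleeding | D |
| 13.1.1.16, aspirin | Yes, its subject | Moderate: caution | Additive salicylate effect | D |

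The different mechanisms may explain the two ratings. They do not tell the reader what to do about aspirin, and no text says which entry governs. No entry defines a time interval for concomitant use.

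**2. What reaches the participant.**

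- Daily aspirin or anticoagulant use: excluded (section 5.2; question 11).
- Any medicine within one hour after a dose: barred (section 4.2, diary, visible insert).
- Aspirin more than one hour after a dose: permitted (sections 4 and 4.2).
- Aspirin before a dose: not addressed in the visible text.

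**3. One day of a compliant as-needed aspirin user.** The participant takes two capsules for a headache, completes the one-hour rating, and takes aspirin as rescue. A second headache follows that day and the participant takes two more capsules. Every step fits sections 4, 4.2 and 6.1 and Appendix B.

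**4. Later checks.** Baseline medications are collected, but shipment depends on the assessment being completed (section 6.1); no review for interactions is described. The diary records other medicines with dose and time, and the adverse event form asks about bleeding. Both come after the event. Section 4.4 cites Appendices B, D, E, F and G for instructions and forms, not A.

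**5. Size.**

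- Maximum exposure: 3 episodes × 2 capsules = 6 capsules (section 6.1; three-episode supply in section 6.6). All 6 may fall on one day. Episodes 2 and 3 are optional, so the minimum for a treated participant is 1 × 2 = 2.
- Active ingredients: 5 (section 2.1). Those with an anticoagulant/antiplatelet entry: willow bark (Major), feverfew (Moderate) and magnesium (Minor), so 3 of 5. For feverfew: "Theoretically, feverfew might have additive effects and increase the risk of bleeding when used with these drugs". For magnesium: "Theoretically, concomitant use of magnesium with anticoagulants or antiplatelets could increase the risk of bleeding".
- Not given in the visible text: the rate of aspirin use and the amount of willow bark per capsule. No expected number of combined exposures or bleeding events can be derived.

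**The case against.** The strongest reply has four parts.

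**Safeguards exist.** Daily aspirin users are excluded, all other medicines are barred for an hour after each dose, and participants with adverse events are told to stop the product (sections 2.2.3 and 6.4). This stands. A reader might infer that neither Appendix A instruction reaches screening, or that the plan only records the combination and never prevents it. The documents do not support that: section 5.2 and question 11 both name aspirin, and the one-hour rule covers it. The gap is confined to as-needed aspirin before a dose or more than an hour after one.

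**The two entries rate different things.** The aspirin entry matches those for the other salicylates (13.1.1.17 and 13.1.1.18), and excluding daily users while allowing occasional use is compatible with caution. This stands in part. It offers a reading under which the plan is coherent, but the plan does not adopt it, and the visible text does not pass on the caution either.

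**The omission cannot be confirmed.** The insert breaks off, screening question 6 and part of the baseline form are broken, and the consent pages and portal FAQs are not in the public copy. This also stands. A reader might infer that participants get no warning at all; the documents cannot show that. What can be shown is that the rescue rule in sections 4 and 4.2 is fully visible and makes no exception.

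**The harm is small.** The interaction is theoretical, 13.1.1.15 itself says willow bark has less antiplatelet effect than aspirin, and GI bleeding is listed only for doses above recommended use (sections 2.2.1 and 6.4.1). This stands and limits the weight of the point.

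**Conclusion.** The point holds as a minor safety clarification. Appendix A gives conflicting advice on one drug pair, and the rescue rule permits what the stricter entry forbids. Expected harm is low and cannot be quantified from the documents, and the rescue rule leaves the primary endpoint untouched.

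The conclusion assumes that some enrolled participants use aspirin as needed, which is plausible in a headache population but not measured in the plan. It also rests on visible text only. A warning in the missing pages would shrink the gap for participants, but the conflict between the rescue rule and Appendix A would remain.

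**What to change.** 1. Before enrolment, the investigator records in writing which Appendix A entry governs aspirin, keeping the stricter one by default.
2. Add to sections 4 and 4.2, the diary reminder and the instructions for use: *Do not take aspirin or a prescribed blood thinner as rescue after a dose, and do not take the test product if you have taken one within [interval set by the investigator].* The documents give no interval, so the investigator must set it. Align the insert, consent and FAQs with the same rule. State whether ibuprofen and other NSAIDs are allowed: the diary scale names ibuprofen, and the magnesium entry (13.1.1.3) lists indomethacin among the anticoagulant/antiplatelet drugs, so a lay reader could not tell. If the aspirin entry is chosen as governing, put a caution in these places instead.
3. Keep the exclusion at daily use and add only *or antiplatelet* to its wording. The term blood-thinning in question 11 may already cover such drugs, so this is a clarification. Do not drop the word daily: 13.1.1.15 counts aspirin in the class, so without it the criterion could exclude occasional aspirin users.

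**Cost.** A sentence in a few places and two added words in one criterion. Rescue choice narrows slightly, some headaches go untreated with the product because aspirin was taken shortly before, and time to other intervention may shift a little among people who would have chosen aspirin.

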6.1 Study Procedures

- Potential participants will review information about the study and complete a screening form.
- During the screening process, the potential participant will be asked questions regarding their symptoms and medical history to ensure that they meet the requirements to participate in this study. Potential participants will also be asked questions to ensure that they do not meet any of the exclusion criteria and meet all of the inclusion criteria.
- After successful screening (participant does not meet any exclusion criteria), participants will review and sign study informed consent.
- Upon verification of signed informed consent, participant will be enrolled into the study.
- At time of enrollment, participant will be given access to the HIPAA compliant study portal.
 - The study portal provides access to study information, signed informed consent form, instructions for product use, frequently asked questions, study surveys, headache diary, and data collection tools.
- Participant shall complete baseline assessments upon access to the portal.
 - O Baseline assessment will include questions regarding the participants' demographics, medications and detailed information regarding their headaches including treatment.
- To ensure that baseline assessments are completed before test product is used by the participant, study materials and study welcome package will be shipped to the participant once the clinical study manager/clinical ops coordinator confirms that the baseline assessment has been completed.
- The welcome package will include an information sheet that will outline instructions for their participation in the trial, the test product, and paper forms of the documents (paper form of study documents will be provided for real time data collection, in the event that the participant cannot log into the study portal to input data).
- Once the participant receives the test product, the participant will log into the study portal to acknowledge the receipt of the test product.
- Study start date will be the reported date of receipt of test product.
- Participant will be sent weekly email reminders that remind them of their participation in the study.
- At the onset of the headache, the participant will start a Headache Diary and complete a 10-point Mankoski pain scale.
 - Onset is defined as the time the participant takes the test product for relief of symptoms.
- After completing the surveys, the participant will take test product. The participant will take 2 capsules with 6-8 oz. of water per headache episode. With a max of 6 pills per day. (If participant takes 6 pills in 1 day this will be defined as 3 headache episodes and the patient will be exited from the study).
- After taking the test product, the participant will complete a Mankoski pain scale at 15 minutes, 30 minutes, and 1 hour after taking the test product.
- Once the participant's symptoms resolve, the participant will complete the headache diary.
- If the participant takes any other medication outside of the test product, the participant will record this on the headache diary.
- After taking the test product, the participant will be instructed to fill out an Adverse Event form for any side-effects experienced.
- After the first headache episode, the participant will be asked to complete the same process for another 2 headache episodes; however, these are not required.
- If the participant completes the required assessments for a total of 3 headache episodes, they will be prompted, by email, to exit the study.

- If the participant only completes the required assessments for the required 1 headache episode, the participant will be prompted, by email, to complete the study exit form and will be exited from the study on day 60 (60 days from the day of receipt of the test product).
- The sponsor nor Hawthorne Effect Inc. will not make any attempt to collect any unused product.
- Upon receipt of study exit survey and review of completed study forms, participant will receive an Amazon gift card of \$25 via email.

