After clicking on an advertisement, potential participants will then be directed to a website where they will complete a screening questionnaire (See *Appendix C*). The screening questionnaire will automatically qualify or disqualify them for study participation. If the participant qualifies, they will be provided an informed consent. Upon completion of the informed consent they will be deemed enrolled in the study.

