6.2 Study Schedule of activities

Assessments	Screening	Consent	Before Receipt of Test Product	Product Received	Event 1	15 Minutes After Event Start	30 Minutes After Event Start	60 Minutes After Event Start
Study Window								
Screening Survey	Х							
Consent		X						
Baseline Survey			Х					
Demographics			Х					
Medications & Supplements			Х					
Acknowledgement of receipt of test product				X				
Headache Diary					X			X
10-point Mankoski Scale					Х	Х	Х	Х
Test Product Consumed					Х			
AE Assessment					X	X	X	X
Study Exit Survey								

Assessments	Event 2	15 Minutes After Event Start	30 Minutes After Event Start	60 Minutes After Event Start	Event 3	15 Minutes After Event Start	30 Minutes After Event Start	60 Minutes After Event Start	Study Exit
Study Window									
Screening Survey									
Consent									
Baseline Survey									
Demographics									
Medications & Supplements									
Acknowledgement of receipt of test product									
Headache Diary	Х			X	Х			X	
10-point Mankoski Scale	X	X	Х	X	X	X	X	X	
Test Product Consumed	Х				X				
AE Assessment	Х	X	Х	X	X	X	Х	X	Х
Study Exit Survey									X

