6.3 Participant Enrollment and Follow-Up

Patients suffering from mild to moderate tension headache symptoms will complete a cloud-based, HIPAA-secured screening survey to determine eligibility. All eligibility criteria must be met for participants to be approved for enrollment in the study. Participants will be provided informed consent and the opportunity to ask questions related to the study procedures, risks and benefits, and rights related to participation in the study. Participants who sign the study informed consent will be prospectively enrolled in the study and provided a link to a patient portal, which provides study resources. Participants will take the study formula at the onset of symptoms and provide information related to pain and tension headache symptoms during the follow-up period. A remote study coordinator may prompt participants to provide study information to ensure that the study forms are completed. Efforts will be taken to ensure minimal withdrawals and loss to follow-up.

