6.7 Study Management

This study uses a decentralized clinical trial format to foster inclusivity, diversity and accessibility for a broad study population and to ensure efficiencies for enrollment and study data collection. The study will be managed using an end to end virtual clinical trial platform called Hawthorne Effect Study Visit Management Platform which is designed to

make patient participation in clinical trials more accessible and as least burdensome as possible. The Hawthorne Effect platform (www.hawthorne-effect.com) is GCP/ICH/21CFR and HIPAA compliant. Hawthorne Effect uses a network of specialty vetted and trained healthcare professionals, or HEROs who are study investigators, screeners and conduct personalized patient visits for screening and follow-up. For this trial, the Hawthorne Effect study visits will be virtual, and the platform will be used to collect patient reported outcomes and to track screening, enrollment and study compliance.

7 Statistical Considerations

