7.3 Analysis Plan

Separate tables will be presented showing the changes from baseline for tension headache severity and functional status at each time point. The changes will be evaluated by the paired-sample t-test. An appropriate nonparametric analysis will also be reported.

Secondary endpoints will be gathered on the subjective experience of these participants related to general health, functional status, personal experience with the products. The secondary endpoints will be self-reported by the participant on their online portal. There will be a questionnaire related to general health, functional status, and the subjective experience of the participant administered at baseline and at study exit.

The purpose of the secondary analyses is to investigate the association between various baseline and other measurements and outcome variables. These secondary analyses are considered hypothesis generating, and the descriptions are somewhat informal. The trial data may suggest secondary analyses not described here.

General statistical methods:

Data will be analyzed using standard statistical methods, as further specified in a statistical analysis plan (SAP), which will be prepared in detail later.

- Data analysis will largely consist of summary statistics and graphs. The only formal group comparisons will be in covariate analyses.
- For continuous variables data presentation will consist of means, confidence intervals computed using the t-statistic, medians, and interquartile ranges. Group comparisons will use t-tests or ANOVA.
- For discrete variables confidence intervals will use the exact intervals, where available.
 Group comparisons will use Fisher's exact test, with the Monte Carlo version used where computationally necessary.
- For time to event variables analysis will use the Kaplan-Meier algorithm, and group comparisons will use the log-rank or proportional hazards methods, depending on the data type.
- Visual analog scale values will be treated as continuous variables. Frequency counts will also be provided for scales with 10 or fewer distinct response levels.
- Covariate analyses will investigate the relation between baseline and outcome variables, using methods appropriate to the data types involved. Age, gender, and baseline medications will be included in these analyses where appropriate data are available.

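### Product may ship once the baseline form is complete, with no visible check of its medication answers against the daily-anticoagulant exclusion

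*Combined protocol and SAP*

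**What the plan says.** **Exclusion and screening.** Section 5.2 excludes people currently on daily anticoagulation medication and gives aspirin, warfarin and heparin as examples. Item 11 of the screening form (Appendix C) asks about this as a yes/no question, and the form qualifies or disqualifies automatically.

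**Enrollment.** Section 5.1: "Upon completion of the informed consent they will be deemed enrolled in the study". Section 6.3 adds: "All eligibility criteria must be met for participants to be approved for enrollment in the study".

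**Baseline.** After enrollment the participant completes a baseline assessment, which Section 6.1 describes as covering "demographics, medications and detailed information regarding their headaches including treatment". The schedule in Section 6.2 has a separate row, "Medications & Supplements", placed before receipt of product.

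**Shipping.** Section 6.1 says that the materials "will be shipped to the participant once the clinical study manager/clinical ops coordinator confirms that the baseline assessment has been completed". The reason given is timing: "To ensure that baseline assessments are completed before test product is used by the participant".

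**Use of the medication data.** Section 7.3 names a statistical use: "Age, gender, and baseline medications will be included in these analyses where appropriate data are available". Section 2.2.2 mentions information for the participant's own clinician.

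**The concern.** By the time staff release product they should hold two self-reports on the same hazard: a yes/no answer from screening and a medication list from baseline. The written shipping condition asks only whether the second report is complete. It does not ask what the report says.

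The two reports can disagree. Item 11 asks people to classify their own drugs, whereas a medication list does not depend on that judgement. A participant on clopidogrel, which Appendix A names but neither Section 5.2 nor item 11 does, could answer No in good faith and then list it. Someone could also start a drug between screening and baseline.

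What is at stake is participant safety. Appendix A describes one serious drug interaction for white willow bark, and it is with this class. Shipment is also the last point at which staff control the product, because Section 6.1 says unused product will not be collected.

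**Working it through.** The plan gives no figure on this point, so the check is mainly a comparison of the procedural text.

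**1. Does any visible step compare baseline medications with Section 5.2 before shipment?**

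| Step | Where | What is checked |
|---|---|---|
| Screening form | 5.1, 5.2, Appendix C item 11 | The exclusion, by automated self-report, before the baseline answers exist |
| Consent | Section 8 | The study manager verifies the signature |
| Approval for enrollment | 6.3 | States that criteria must be met; sets out no later comparison |
| Platform tracking | 6.7 | "the platform will be used to collect patient reported outcomes and to track screening, enrollment and study compliance"; no comparison of medication answers is described |
| Shipment | 6.1 | Completion of the baseline assessment |
| Day-30 contact | 6.5 | Only people who have reported no event, with product already in hand |
| Review of completed forms | 6.1 | At exit, before the gift card |

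None of these compares the baseline medication answers with the exclusion while staff still hold the product.

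**2. How serious is the interaction, on the plan's own account?**
- Willow bark with anticoagulant or antiplatelet drugs (Appendix A, 13.1.1.15): Major, severity High, occurrence Probable, evidence level D.
- The introduction to the willow bark entries calls the interaction anecdotal.
- Aspirin has its own entry (13.1.1.16), rated Moderate, although 13.1.1.15 also lists it.
- Feverfew with the same class (13.1.1.19): Moderate, severity High, level D.

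**3. Largest exposure.** Section 6.6 supplies three episodes and Section 6.1 gives two capsules per episode: 3 × 2 = 6 capsules. Section 6.1 allows all six in one day.

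**4. Effect on the trial's numbers.** Section 7.2 assumes that 50% of participants have a headache in the period, and Section 5.1 wants 97 treated. With all 200 shipped, 200 × 0.5 = 100. With six withheld, (200 − 6) × 0.5 = 97, still the desired number. With seven withheld, 193 × 0.5 = 96.5. The 68 patients in Section 7.2 reproduce: for a mean change of 2 and an SD of 5, exact paired-t power is 90.2% at two-sided 0.05 (the level is assumed, as none is stated). Nothing here alters that calculation.

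**5. Staff time.** Section 5.1 caps enrollment at 125% of target: 1.25 × 200 = 250. Assuming 1 to 2 minutes per form, the range runs from 200 × 1 = 200 minutes (3.3 hours) to 250 × 2 = 500 minutes (8.3 hours).

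**6. Number affected.** The documents give no rate of disagreement between item 11 and the baseline list, and no basis for one. No estimate is offered.

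**The case against.** The strongest reply is that the exclusion is already enforced. Item 11 puts the question directly, with aspirin and warfarin as examples; a Yes disqualifies automatically; and Sections 2.2.3 and 6.3 say that people who meet exclusion criteria are not enrolled. This stands. A reader might infer that nobody checks the exclusion at all, and the documents contradict that. What is missing is a second check, on data already collected.

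The group concerned is also narrow: people who answer No and then list such a drug, or who start one in between. Portal access comes at enrollment, so the interval before baseline is probably short.

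Third, some of the relevant text cannot be read. The baseline form (Appendix D) breaks off after item 9d and resumes just before item 14, which is where medication items would be expected. The consent pages and part of the appendices are also unavailable. A stop message could sit in any of these. For that reason it would go too far to say that a participant listing warfarin would certainly be shipped product. Section 6.1 says when shipping happens; it does not tell staff to ship in the face of a known exclusion. The text supports could, and no more.

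Finally, the evidence is weak and the dose small, as the working shows. That limits the priority of the point. It does not remove it, because the sponsor's own appendix advises against the combination.

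**Conclusion.** The point holds as a low-probability, bounded safety gap in a second check. Completion of the baseline assessment is the only visible condition for shipment, so a disqualifying medication answer could be on file when product leaves. The worst exposure is six capsules per affected person, on level D evidence. There is no material effect on the primary analysis.

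The conclusion rests on two assumptions: that the baseline form collects routine medications, which Sections 2.2.2, 6.1 and 6.2 indicate, and that the unreadable text contains no stop rule. If it does contain one, the change below simply brings Section 6.1 into line with it. The change is worth making because it is nearly free and acts at the last moment of control, not because many participants are expected to be affected.

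**What to change.** In Section 6.1, keep the existing shipping condition and add after it:

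> and that its medication answers show no Section 5.2 exclusion; any anticoagulant or blood-thinning drug listed as taken daily (including aspirin and, given Appendix A 13.1.1.15, other antiplatelet drugs such as clopidogrel) is referred to the investigator before shipment.

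State openly that naming antiplatelet drugs other than aspirin clarifies Section 5.2, whose examples do not include them. The clarification follows the blood-thinning wording of item 11 and the drugs listed in Appendix A. The word daily keeps to Section 5.2, so occasional aspirin for headache does not trigger a referral.

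The cost is one clause in a check that the same staff already make: about 3 to 8 hours in total at the assumed 1 to 2 minutes per form. A few shipments may be delayed or withheld. Up to six withheld out of 200 would still leave 97 expected treated participants under the plan's own 50% assumption.
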